High-gamma amplitude will be calculated using an approach that utilizes the Hilbert transform. Specifically, the signal will be filtered into 8 subbands, logarithmically spaced between 70-150 Hz. For each subband, we will calculate the amplitude (absolute value) of the analytic signal, which is estimated using the Hilbert transform. Each subband will be normalized to its baseline mean and standard deviation, estimated across trials. The HGA estimate is then the mean across these subbands.

We will use *least-squares linear regression neural encoding models* to investigate relationships between acoustic stimulus dimensions and STP neural responses during the baseline quiet context, in which stimuli sample a 2-d F0 x VOT grid. This approach will allow us to identify the subset of electrodes and temporal windows that encode at least one of these 2 dimensions at baseline; targeted analysis on this subset (described below) will then be used to compare listening contexts.

Encoding model inputs will consist of F0 and VOT, with an output of channel- and time-specific HGA. For a given electrode, individual models will be built using single trial data and a sliding window, allowing us to identify the temporal window relative to stimulus onset that yields significant models. Model quality will be assessed in two ways. First, using models built on all trials, we will calculate the regression *F*-statistic, which determines if any coefficients are significant. This will be compared to null distributions estimated with permutation tests that shuffle data across trials. Second, goodness-of-fit will be assessed for significant models by performing leave-one-out cross-validation and calculating R^2 , the proportion of variance in neural activity explained by the model. Finally, we will assess the relative encoding strength of each acoustic dimension using model coefficient *t*-statistics. In summary, this approach will allow us to identify the timing and anatomical location of F0 and VOT encoding during baseline quiet listening conditions for which dimensions are sampled orthogonally (as in **Figure 1a**).

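### Leave-one-out R-squared is computed only for models already selected by F on the same trials, so it is not independent evidence of encoding, and the permutation family for that F search is not stated

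*SAP*

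**What the plan says.** The encoding models are set out in the SAP, Evaluating the Hypotheses: Neural Analyses.

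- **Model.** "Encoding model inputs will consist of F0 and VOT, with an output of channel- and time-specific HGA". For each electrode, "individual models will be built using single trial data and a sliding window".
- **First quality check.** "using models built on all trials, we will calculate the regression *F*-statistic, which determines if any coefficients are significant". On the reference distribution: "This will be compared to null distributions estimated with permutation tests that shuffle data across trials". The stated purpose includes "allowing us to identify the temporal window relative to stimulus onset that yields significant models".
- **Second quality check.** "goodness-of-fit will be assessed for significant models by performing leave-one-out cross-validation", with R-squared as the proportion of neural variance explained. The section reserves no trials and describes no nested selection.
- **Use.** The approach is meant to "identify the timing and anatomical location of F0 and VOT encoding during baseline quiet listening conditions". The next part of the section limits the Baseline/Canonical and Canonical/Reverse cluster tests to channels and windows that were significant at Baseline.
- **Multiplicity.** The closing Rigor and Reproducibility paragraph commits to control for multiple comparisons. It gives no method, family or level, and does not say whether sliding windows and electrodes are covered.

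**The concern.** The SAP presents two assessments of model quality, and a reader will take the second as a check on the first. Leave-one-out cross-validation gives an honest estimate of prediction for a model fixed in advance. Here the electrode and window are chosen on all the trials before the cross-validation starts, so every held-out trial has already helped to pick the model that it then scores.

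Two things follow. A window that passed F by chance will usually return a positive cross-validated R-squared, which looks like corroboration. And the R-squared reported for weak true sites is too high, because weak sites enter the report only when chance has helped them over the threshold.

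A related gap concerns the map itself. With many overlapping windows on each of many electrodes, its error rate depends on the permutation family, which is not stated. This bears on H6 versus H7, which turn on whether adaptive effects are seen in HG or only at higher levels of the cortical hierarchy.

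**Working it through.** **Inputs.** From the SAP: two predictors; one model per electrode and window; selection by F on all trials; leave-one-out only for significant models. Assumed, because the documents do not give them: an intercept, a 5x5 F0 by VOT grid, trial counts of 50 to 500, 20 to 50 windows, correlation between adjacent windows, normal errors, and a 5% level for each F. The SAP's only computed design figure, N=25, concerns the behavioral effect, so there is no figure to reproduce for this step.

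**Step 1: what F gives a positive leave-one-out R-squared?** In general R²_LOO = 1 - Σ[e_i/(1-h_ii)]²/SST. With three coefficients the mean leverage is 3/n. Treating leverages as equal,

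R²_LOO = 1 - (1-R²)/L, with L = (1-3/n)².

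This is positive when F > [(1-L)/2]/[L/(n-3)].

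- n=100: L = 0.97² = 0.9409, so F > 0.02955/0.00970 = 3.05. The 5% critical value is 3.09.
- n=500: L = 0.994² = 0.98804, so F > 0.005982/0.001988 = 3.01. The 5% critical value is 3.01.

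If the denominator uses leave-one-out means, the threshold falls to about F > 2, and every model that passes is positive.

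**Step 2: size at null windows.** With no true encoding, P(R²>c) = (1-c)^((n-3)/2), so the 5% cut-off is 1-c = 0.05^(2/(n-3)). Among windows that pass, the mean of 1-R² is (1-c)(n-3)/(n-1); among all windows it is (n-3)/(n-1). Dividing by L and subtracting from 1:

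| Trials | 1-c | Mean R²_LOO, passed F | Mean R²_LOO, unselected |
|---|---|---|---|
| 100 | 0.9401 | 1 - 0.9211/0.9409 = +0.021 | 1 - 0.9798/0.9409 = -0.041 |
| 200 | 0.9700 | 1 - 0.9603/0.9702 = +0.010 | 1 - 0.9899/0.9702 = -0.020 |
| 500 | 0.9880 | 1 - 0.98406/0.98804 = +0.004 | 1 - 0.99599/0.98804 = -0.008 |

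Simulation of null electrodes with the grid's unequal leverages agrees. About 95-98% of selected null windows are positive (90-99% across all settings tried), against about 5-7% of unselected ones.

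**Step 3: the same fits scored on new trials.** With an equal number of fresh trials, selected null windows have mean R-squared of about -0.20 (50 trials), -0.09 to -0.11 (100), -0.04 (250) and -0.02 (500). About 3-8% are above zero.

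**Step 4: does a stricter F threshold repair R-squared?** No. With 100 trials, 20 windows and correlation 0.9, the 5% maximum-F cut-off is 5.62. Then c = 11.24/108.24 = 0.1038, and the mean among windows at the cut-off or above is 1 - (0.8962 × 0.9798)/0.9409 = +0.067 (simulation +0.068). In the runs with 20 or 50 windows, all remaining false positives were positive.

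**Step 5: weak true sites.** At 100 trials and true R-squared 0.02, selected sites averaged +0.034 in one set-up and +0.047 in another. The direction is stable; the size depends on the set-up.

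**Step 6: the F search, if windows were left uncorrected.** The share of null electrodes with at least one significant window is about 30-60% with 20 windows and about 50-85% with 40, depending on correlation. For independent windows it is 1 - 0.95^20 = 0.64 and 1 - 0.95^40 = 0.87. A maximum-F threshold over windows returns the rate to about 4-6% per electrode. Held at 5% per electrode, that still gives 50 × 0.05 = 2.5 expected false electrodes among 50, and 1 - 0.95^50 = 0.92 probability of at least one (independent electrodes assumed).

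**The case against.** The best defense has four parts.

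1. **Multiplicity control is promised.** The SAP commits to it and refers to pre-registered analyses that are not in these documents. The wording on shuffled null distributions does not exclude a maximum over windows. This stands. A reader might infer that 30-85% of null electrodes will be mapped as encoding; the documents do not support that, since those rates apply only if windows go uncorrected. The fair criticism is that the control is unspecified for this step. The contrast within the SAP is notable: the Canonical/Reverse comparison gets a detailed maximum-cluster procedure and the encoding search gets none.

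2. **R-squared is descriptive.** It is called goodness-of-fit for models already significant, and no threshold on it admits a site. This also stands. A reader might infer that the cross-validation creates false sites, or that they get in by passing both checks. False mapping comes from the F search; the cross-validation only fails to reveal it.

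3. **The bias is small.** Over all selected null windows it is about 0.02 at 100 trials and 0.004 at 500. True, although weak real effects may be of similar size.

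4. **Later tests are protected.** For Canonical versus Reverse, selection uses Baseline trials and the test permutes context labels, so false sites mainly dilute power and do not manufacture context effects. This stands. Reuse of Baseline trials in Baseline versus Canonical is a separate question, not assessed here.

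None of this makes leave-one-out R-squared, computed after selection on the same trials, an independent check.

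**Conclusion.** The point holds in a limited form. As written, the second quality check adds almost no evidence beyond the first: about 95-98% of null windows that pass F at 5% also show a positive leave-one-out R-squared. The reported values are biased upward for null and weak true sites, whichever multiplicity method is used. The bias is modest and shrinks with more trials. Separately, the multiplicity commitment needs a stated family and level before the error rate of the encoding map can be known.

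All rates are scenario figures that rest on the assumed grid, trial and window counts, correlations and 5% level. The near-coincidence of the two F thresholds is less fragile: it follows from having two predictors plus an intercept and a 5% test.

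It would go too far to call the map inflated as a matter of fact, or to say that held-out scoring alone makes false sites disappear. Some 3-8% of selected null windows stay above zero on new trials, and R-squared removes no site unless a rule is added. The plan should be amended before analysis; nothing here undermines the design.

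**What to change.** 1. **State the permutation family and level for the encoding F.** Apply each planned trial shuffle jointly to all windows and electrodes, and compare the observed F with the permutation distribution of the maximum F over both. A cluster statistic over the same family would also serve. Control within each electrode alone is not enough (Step 6).
2. **Take window choice out of the scored data.** Choose the window inside the training folds, or on one half of the trials and score on the other.
3. **Report R-squared for every electrode in the pre-set regions, including the control sites outside STP,** not only for significant models. The control sites then give an empirical view of what null electrodes look like.
4. **Do not describe post-selection R-squared as confirmation of encoding.** If it is kept, label it as computed after selection on the same trials.

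Cost: code and SAP wording; no new data. Fewer electrodes will qualify, and reported R-squared values will be smaller and, if trials are split, less precise.

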Evaluating the Hypotheses: Behavioral Analyses. We will evaluate the behavioral impact of the VOT and F0 acoustic dimensions on classification using *mixed-effects logistic regression* (with patient as a random effect, stimulus VOT and F0 as fixed effects and classification responses as the outcome). Following our prior work,^{14,25-29} perceptual weights for the dimensions will be computed for each patient as the correlation between dimension values and the proportion of *peach* classifications across all stimuli in the VOTxF0 stimulus grid with absolute values of the correlation coefficients normalized to sum to one as an *index of relative perceptual weight* in quiet (Aim 1) and in noise (Aim 2). To examine the impact of a change in 'accent' in the DBSL paradigm, we will use mixed logit models with responses as a function of patient, block, test stimulus F0 and the interaction between block and F0 (Aim 2). Patient will be modeled as a random effect, with the other factors as fixed effects.

Evaluating the Hypotheses: Neural Analyses. We will take a multi-pronged analysis approach. Our pilot data in **Figure 3** demonstrate that *high-y* activity (HGA) is modulated by graded acoustic details across the VOT and F0 dimensions across electrodes placed in the STP. Following the analysis pipeline used in our pilot data analyses, we will specifically examine stimulus-time-locked HGA to the *Test* stimuli, which possess consistent, perceptually-ambiguous VOT and differentiated F0. We have specific, directional predictions (detailed above)

regarding how HGA to F0-differentiated *Test* stimuli will vary according to perceptual weight in behavior. To briefly recap, we expect that HGA to *Test* stimuli will be better differentiated (1) in the Speech-in-Noise compared to the Clear baseline context (because F0 carries greater perceptual weight); (2) in the Canonical, compared to the Reverse, context; (3) in the Canonical, compared to the Baseline Clear Speech context (because stimulus statistics exaggerate the dimension regularity in behavior).

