To characterize shifts in neural encoding across listening contexts, we will investigate Noise using encoding models and Canonical/Reverse contexts using *cluster-based approaches*.^{32,49} Encoding models will be built from the Noise context for all channels and timepoints, using the same approach as Baseline. If a channel/timepoint is significant in either Baseline or Noise, the F0 and VOT coefficient *t*-statistics will be compared across contexts. We hypothesize that encoding of F0 will strengthen and VOT will weaken in Noise, as measured by changes in *t*-statistic magnitudes across multiple models. Next, we will compare neural responses for each of the two *Test* stimuli (which were embedded in the F0 x VOT grids, **Figure 1a**) between Baseline vs. Canonical and Canonical vs. Reverse. The clustering approach will look only at Baseline significant channels and time windows and involves randomly assigning listening context labels to single-trial data followed by a *t*-test at each time step. Across all permutations, a criterion value will be established for each timepoint (>95% of absolute value of *t*). For each of these permutations, we will next determine whether its value exceeds criterion across timepoints, and for how many timepoints it exceeds criterion (a 'cluster'). For each cluster, *t* values will be summed and assigned to all points in the cluster, with the largest summed cluster value stored for each permutation. This will create a null distribution of 1000 cluster values. We then will establish whether the cluster size calculated across real neural data (organized according to listening context) exceeds the 95% permutation-based cluster values such that $p < .001$ indicates an observed cluster is greater than all permutation-based clusters. Using this approach, we will identify context-dependent shifts in HGA responses, which we predict will reflect observed shifts in perceptual weights. Namely, we hypothesize that HGA responses in F0-encoding channels will be enhanced in the Canonical context relative to both Baseline and the Reverse context.

Rigor and Reproducibility. Analyses will be controlled for multiple comparisons, with sex as a co-variate in our analyses. We will use pre-registration and provide access to all the deidentified source data.

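### The predicted better separation of the Test stimuli in Noise has no matching test: Noise is analysed only by a whole-grid encoding model, whose F0 coefficient measures something else

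*SAP*

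**What the plan says.** All of this is in the SAP, under Evaluating the Hypotheses: Neural Analyses.

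- **The prediction.** The plan focuses on HGA to the Test "stimuli, which possess consistent, perceptually-ambiguous VOT and differentiated F0". It gives three directional predictions for how well HGA separates them. The first is better separation "in the Speech-in-Noise compared to the Clear baseline context (because F0 carries greater perceptual weight"). The second and third concern Canonical against Reverse and Canonical against Baseline.
- **The method for each context.** The plan states that "we will investigate Noise using encoding models and Canonical/Reverse contexts using" cluster-based methods. For Noise: "Encoding models will be built from the Noise context for all channels and timepoints, using the same approach as Baseline".
- **The model.** "Encoding model inputs will consist of F0 and VOT, with an output of channel- and time-specific HGA". No F0 × VOT term is named. The fit uses every trial in the context: "First, using models built on all trials, we will calculate the regression" F-statistic. The Noise hypothesis (F0 encoding stronger, VOT encoding weaker) is judged by changes in the size of the coefficient t-statistics.
- **The direct Test-stimulus comparison.** It is made "between Baseline vs. Canonical and Canonical vs. Reverse". Noise is not in that list.

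**The concern.** Predictions two and three each have a comparison of the Test stimuli between the contexts they name. Prediction one has none. Its only neural analysis is an F0 coefficient taken over the whole grid, in which the Test stimuli are just some of the cells.

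The two quantities answer different questions. The prediction is about the F0 effect at one ambiguous VOT value. The coefficient is the F0 effect averaged over all VOT values. They agree if the F0 effect is the same at every VOT, and they can part company if it is not. A report could then show F0 up and VOT down in Noise, and be taken as support for prediction one, although separation of the Test stimuli had not changed.

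**Working it through.** **No plan figure to reproduce.** The only related number is N=25, which rests on effect sizes in a figure that is not shown. This point does not depend on it.

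**Step 1: predictions against tests.**

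| Prediction for the Test stimuli | Direct Test-stimulus comparison in the SAP |
|---|---|
| (1) Noise better than Baseline | none |
| (2) Canonical better than Reverse | Canonical vs. Reverse |
| (3) Canonical better than Baseline | Baseline vs. Canonical |

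This gap needs no assumption.

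**Step 2: what the F0 coefficient measures.** The SAP describes Baseline as "during baseline quiet listening conditions for which dimensions are sampled orthogonally", and Noise is modelled the same way. On a balanced grid the F0 slope in HGA ~ F0 + VOT equals the mean of the F0 slopes within each VOT level.

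**Step 3: a case where the two quantities separate.** Assumptions, none from the documents: response = logistic(A × VOT + F0), both dimensions coded −1 to 1, Test stimuli at VOT = 0 with F0 = ±1. Noise weakens VOT, so A falls from 4 to 2.

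Test-stimulus difference: logistic(1) − logistic(−1) = 0.731 − 0.269 = 0.462. It does not contain A, so it is identical in both contexts.

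F0 slopes within each VOT level on a 5-step grid:

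| VOT | −1 | −0.5 | 0 | 0.5 | 1 | Mean |
|---|---|---|---|---|---|---|
| A = 4 | 0.020 | 0.110 | 0.234 | 0.110 | 0.020 | 0.099 |
| A = 2 | 0.110 | 0.191 | 0.234 | 0.191 | 0.110 | 0.167 |

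Nothing changes at VOT = 0. The mean rises because cells away from the boundary become ambiguous.

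| Grid | F0 slope, A = 4 to 2 | Change | VOT slope, A = 4 to 2 | Change |
|---|---|---|---|---|
| 5 × 5 | 0.099 to 0.167 | +69% | 0.527 to 0.373 | −29% |
| 7 × 7 | 0.105 to 0.173 | +65% | 0.547 to 0.381 | −30% |
| 9 × 9 | 0.108 to 0.176 | +63% | 0.558 to 0.386 | −31% |

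The SAP compares t-statistics, and these move the same way. With a 5 × 5 grid, 10 trials per cell and residual SD 0.5, expected F0 t goes from 2.17 to 3.73 and VOT t from 11.59 to 8.31.

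**Step 4: dependence on steepness.** On the 7-step grid, A from 2 to 1 takes the F0 slope from 0.173 to 0.215 (+24%), and A from 1 to 0.5 takes it from 0.215 to 0.230 (+7%). In the other direction, A from 6 to 1.5 on the 5-step grid takes it from 0.068 to 0.190 (2.8 times).

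**Step 5: cases where they do not separate.** With a linear response the F0 slope stays at 0.300 and its t at 6.71 when VOT weakens. With a sigmoid in VOT plus a linear F0 term the slope also stays at 0.300. Its t rises only from 6.09 to 6.70, because lack of fit shrinks.

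**Step 6: behavior of the missing test.** In 4,000 simulated channels per scenario with an unchanged Test-stimulus difference, a direct Noise-minus-Baseline contrast rejected in 5.1–5.4% (nominal 5%), under both the linear and the logistic response. The whole-grid comparison reported stronger F0 in 2.1% of channels under the linear response. Under the logistic response with A from 6 to 1.5 it did so in 50% (residual SD 0.5) and 96% (SD 0.25).

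**The case against.** The strongest reply is that the whole-grid model is the right readout for H3. The hypotheses are about cortical response reflecting perceptual weight as measured in behavior. The SAP's Behavioral Analyses define that weight from correlations over the entire VOT × F0 grid, in quiet and in noise. Apply that index to Step 3 on the 7-step grid. At A = 4 the correlations are 0.184 (F0) and 0.957 (VOT), so the relative F0 weight is 0.184 / (0.184 + 0.957) = 0.161. At A = 2 they are 0.410 and 0.902, giving 0.410 / 1.312 = 0.312. Behavioral F0 weight nearly doubles, so a percept-following site whose whole-grid F0 slope rises is tracking a real shift. This stands. A reader might infer that the Noise encoding analysis gives a false answer to H3 and should be demoted. The documents do not support that.

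Second, a reader might infer that the F0 coefficient must rise whenever VOT becomes less informative. It need not (Step 5). The SAP describes pilot HGA as graded across both dimensions, which does not settle the shape.

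Third, the list of predictions is offered as a short recap, the encoding section states its own matching Noise hypothesis, and the SAP points to pre-registered analyses and a proposal section that are not among these documents. A Noise contrast may be specified there. That is possible, but this SAP describes none, and its own recap names the Test stimuli as the object of the Noise prediction.

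**Conclusion.** The concern holds in this form: prediction one, about the Test stimuli in Noise, has no matching analysis in the SAP, and the whole-grid F0 coefficient is not a substitute for one. The first part follows from the text alone. The second is conditional. If HGA at a site is categorical or saturating in VOT, the F0 slope can rise by 63–69% in the worked case (about 7% to 2.8-fold over the settings tried) with no change at the Test stimuli. If F0 coding is linear or additive, the slope does not change. Response shape, grid size, trial counts and residual SD are assumptions, since the documents do not give them.

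The whole-grid comparison remains a legitimate test of whether neural encoding follows the whole-grid behavioral weight. What it cannot show by itself is better separation of the Test stimuli.

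**What to change.** 1. Add a test of prediction one. On single trials, take (high-F0 minus low-F0 Test stimulus) in Noise minus the same difference in Baseline, and refer it to a permutation distribution. The existing cluster procedure compares contexts for each Test stimulus separately, so it needs adapting: the statistic must be the difference between the two stimuli, so that a general shift of HGA in Noise does not count as better separation. State the channels and time windows in advance.
2. Keep the whole-grid encoding comparison and name it as the neural counterpart of the whole-grid behavioral weight index.
3. State that a whole-grid F0 rise will not be reported as better Test-stimulus separation.

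**Cost.** SAP text and some code. No new data should be needed: the SAP says the Test stimuli are embedded in the grids, and the protocol's study design says every block includes test stimuli. The multiplicity control gains one comparison.

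Precision falls because only Test-stimulus trials are used. With m trials in every cell, the Test difference per unit of F0 has SE σ/√(2m), against σ/√(m ΣF0²) for the whole-grid slope. On a 5 × 5 grid ΣF0² = 5 × 2.5 = 12.5, so the ratio is √(12.5/2) = 2.5. On a 7 × 7 grid ΣF0² = 21.8 and the ratio is 3.3. If the Test stimuli are presented more often than other cells, the loss is smaller.

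### The SAP predicts that the two Test stimuli will be better differentiated in Noise than in Clear speech, but the only Noise analysis it states is a regression over the whole F0 x VOT grid, which answers a different question

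*SAP*

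**What the plan says.** All of this is in the SAP, Evaluating the Hypotheses: Neural Analyses.

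- **Target.** The SAP states that "we will specifically examine stimulus-time-locked HGA to the *Test* stimuli, which possess consistent, perceptually-ambiguous VOT and differentiated F0".
- **Prediction (1).** "we expect that HGA to *Test* stimuli will be better differentiated (1) in the Speech-in-Noise compared to the Clear baseline context". The reason given is that F0 carries more perceptual weight in noise. Predictions (2) and (3) concern Canonical against Reverse and Canonical against Baseline.
- **Baseline model.** The SAP uses "least-squares linear regression neural encoding models" on single trials from the F0 x VOT grid. "Encoding model inputs will consist of F0 and VOT, with an output of channel- and time-specific HGA". No F0 x VOT term is mentioned.
- **Noise model.** "Encoding models will be built from the Noise context for all channels and timepoints, using the same approach as Baseline". At any channel and timepoint significant in either context, the F0 and VOT t-statistics are compared, with F0 expected to strengthen and VOT to weaken.
- **Test-stimulus contrasts.** The cluster-based permutation analysis compares the Test stimuli for Baseline against Canonical and for Canonical against Reverse. Noise is not in that list.

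The Test stimuli are described as embedded in the grids, and the Protocol (Study Design, item 2) has test stimuli in every block.

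**The concern.** Prediction (1) concerns the F0 effect at one ambiguous VOT. The Noise analysis estimates an F0 effect averaged over all VOT levels and judges it by the size of a t-statistic. The two can move independently. An analyst who follows the SAP could report stronger F0 encoding in Noise and be read as having confirmed prediction (1), although the Test-stimulus comparison was never made. The reverse error is also possible: a real change confined to the Test VOT would be diluted in the grid average.

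**Working it through.** The SAP gives no expected size for the Noise effect, so there is no figure to reproduce. N=25 comes from behavioural effect sizes in a figure and plays no part here.

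**1. Predictions set against stated tests**

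| Prediction about the Test stimuli | Stated test on the Test stimuli |
|---|---|
| (1) Noise vs Clear baseline | none; grid regression only |
| (2) Canonical vs Reverse | cluster permutation test |
| (3) Canonical vs Baseline | cluster permutation test |

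**2. What the grid coefficient measures.** In a balanced grid, the F0 coefficient of an additive least-squares fit is the mean of the F0 slopes within each VOT level. It determines the Test difference only if F0 acts linearly and equally at every VOT.

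**3. Illustration when HGA is not linear.** The documents give none of these inputs, so all are assumed:
- mean HGA = g x logistic(a·VOT + b·F0), with cues scaled -1 to 1;
- 5x5 grid, 10 trials per cell, residual SD 1;
- Test stimuli at VOT = 0 and F0 = ±1, with b = 1.5 in both contexts;
- 25 patients, one site each, gain varying by 30% (SD) between patients, SD of b 0.3 by patient and context.

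True Test difference (g = 1) = logistic(1.5) - logistic(-1.5) = 0.818 - 0.182 = 0.635, whatever the value of a.

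Grid F0 slope (g = 1), as the mean of the five within-VOT slopes:
- a = 6: (0.005 + 0.083 + 0.326 + 0.083 + 0.005)/5 = 0.100
- a = 3: (0.083 + 0.226 + 0.326 + 0.226 + 0.083)/5 = 0.189
- a = 1.5: (0.226 + 0.297 + 0.326 + 0.297 + 0.226)/5 = 0.274

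The middle term, the slope at the Test VOT, is 0.326 throughout. The average still rises 1.9-fold (0.189/0.100) or 2.7-fold (0.274/0.100).

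The table shows rejection rates of a nominal 5% test. The last column is the SAP's own behavioural index: the F0 correlation over the grid divided by the sum of the F0 and VOT correlations. For a = 3 it is 0.377/(0.377 + 0.899) = 0.30.

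| VOT weight, Baseline to Noise | Grid F0 slope test, g = 1 | Same, g = 0.5 | Test contrast | SAP index of F0 weight in Noise |
|---|---|---|---|---|
| 6 to 6 | about 5% | about 5% | about 5% | 0.15 |
| 6 to 4 | 40% | 14% | 4-7% | 0.22 |
| 6 to 3 | 87% | 36% | 4-7% | 0.30 |
| 6 to 1.5 | 100% | 89% | 4-7% | 0.50 |

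Repeat runs agreed within a few percentage points. If HGA is strictly linear and additive, the slope does not inflate.

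**4. The t-statistic itself.** This second illustration uses slopes linear in F0 (5x5 grid, 10 repeats, 250 trials). A Baseline slope of 0.2 gives a mean F0 t of 2.26 and a true Test difference of 2 x 0.2 = 0.40.

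| Change in Noise | Mean F0 t | True Test difference |
|---|---|---|
| slope 0.5 except at the Test VOT | 4.92 | 0.40 |
| slopes unchanged, residual SD halved | 4.51 | 0.40 |
| slope 0.8 at the Test VOT only | 3.51 | 1.60 |
| slope 0.5 everywhere | 5.60 | 1.00 |

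The t-statistic more than doubles in two cases where the Test difference is fixed. It rises less (3.51/2.26 = 1.6-fold) where the Test difference quadruples.

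**5. Limits of a Test contrast** (logistic model, g = 1).
- Power: if b rises from 1.5 to 3, the Test contrast rejects about 55% of the time and the grid test about 95%.
- Boundary shift: add an intercept c in Noise. With b unchanged and c = 1.5, the Test difference becomes logistic(3) - logistic(0) = 0.953 - 0.500 = 0.453. With the VOT weight falling from 6 to 3, the contrast then rejects about 26% of the time in the wrong direction.
- With b rising to 2.5 and c = 2, the difference is logistic(4.5) - logistic(-0.5) = 0.989 - 0.378 = 0.611, close to 0.635. The Test contrast rejects about 6-7% of the time and the grid test about 100%.

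**The case against.** The strongest reply is that the grid analysis is the natural test of the Noise hypotheses. The SAP defines perceptual weight over all stimuli in the grid, in quiet and in noise, and the encoding model is its neural counterpart. A reader might infer from the 40%, 87% and 100% that the grid test gives false positives while F0's weight has not changed. The documents do not support that. Only the logistic coefficient b is held fixed. The SAP's own index of F0 weight rises from 0.15 to 0.22, 0.30 and 0.50 in the same scenarios, so for H3 and for the stated expectation that F0 strengthens and VOT weakens, those rejections are correct. This part of the reply stands.

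A reader might also infer that the Test contrast should replace the grid model. That does not follow either: a boundary shift in Noise can hide a real F0 rise from the Test contrast, and its power is lower.

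Three further points stand as limits:
- The SAP describes pilot HGA as following graded acoustic detail, so a saturating response is not established.
- The simulation tests slopes at one unselected site per patient, whereas the SAP compares t-statistic magnitudes at selected sites. With t-magnitudes at gain 0.5, the rates are 7%, 29% and 82%.
- The SAP points to an Approach section and to pre-registered analyses that are not available here and could contain the missing contrast.

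None of this supplies a Noise contrast on the Test stimuli in the SAP as written. Its general statement that Test-stimulus HGA will be examined does not do so, because the contrasts are then listed and Noise is left out.

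**Conclusion.** The point holds as a mismatch between one stated prediction and the analysis assigned to it. In these documents, prediction (1) has no test on the stimuli it names. This finding rests on the text alone and needs none of the assumed numbers.

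How far the grid result could mislead about the Test stimuli depends on the response shape. There is no slope inflation if HGA is linear and additive, although the t-statistic can still move with residual variance. If HGA follows a logistic in both cues and VOT weight falls, the grid test can reject in anything from a small fraction to nearly all runs with the Test difference unchanged. A weaker VOT in Noise is what the SAP itself expects. That the model is additive is inferred from the two listed inputs, and that Noise uses the whole grid is inferred from its following the Baseline approach.

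The grid comparison remains valid for relative F0 and VOT encoding. The gap should be closed before analysis, but it does not undermine the Noise aim as a whole.

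**What to change.** Add to the SAP's neural analyses a Noise-versus-Baseline by F0 contrast on the Test-stimulus trials: the HGA difference between the two Test stimuli in Noise minus the same difference in Baseline. Using all F0 steps at the Test VOT is an alternative that should recover some power, though this was not simulated. State which channels and time windows are eligible, and include the contrast in the multiplicity control. Base any statement that the Test stimuli are better differentiated in Noise on this contrast. Keep the grid encoding comparison as the test of relative F0 and VOT encoding in Noise.

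The change needs a few sentences of SAP text and no new patients. It should need no new trials, since the Protocol puts test stimuli in all blocks. The costs are one more comparison, lower power than the grid model (about 55% against 95% under the assumptions above) and sensitivity to a category-boundary shift. A null Test contrast should therefore be read alongside the grid result and the behavioural boundary in Noise.
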